Real World Testing of an Artificial Intelligence-enabled App as an Early Intervention and
Support Tool in the Mental Health Referral Care Pathway

NCT05533190

8 August 2023

Methods

Randomisation – sequence generation

Demographic data was collected from all patients immediately after completion of the informed consent process, over the phone. Together with data from the IAPT referral, this information was used in the randomisation algorithm to ensure that the intervention and control arms were balanced on key variables (gender, age, ethnicity, self-reported antidepressant use, and severity of depression).

Randomisation – allocation concealment mechanism

Consenting participants were inputted into a masked computer randomisation algorithm and the outcome was recorded in an electronic record to conceal treatment allocation from study researchers. Participants were sent an automatic email to inform them of their group assignment, and participants in the intervention arm will receive the link to download Wysa.

Randomisation – implementation

Psychology assistants recruited specifically for the trial and covering the three London Community Living Well Service sites enrolled participants in the study. A computer generated the random allocation sequence assigned participants to interventions, with a ration of 2:1 randomization to the intervention group.

Blinding

Due to the nature of the intervention, no blinding of participants was possible in the study, as all participants knew whether they were using the app. Clinical treatment teams were not blinded as they knew through the electronic patient record if a participant has received the intervention. The evaluation team will be blinded to treatment using the randomisation algorithm.

Statistical methods

Descriptive statistics was used to assess baseline comparability and the distributions of the primary and secondary outcomes. Visualisations via density and box plots supplemented the tabulations. Linear regression was used to carry out comparative analysis of the primary outcome PHQ9, and secondary outcome GAD7, to compare the two treatment arms. For the primary outcome, PHQ9, the study was powered to detect a clinical meaningful difference of 2 points, with 80% power and a Type 1 error rate of 0.05. Additional post hoc regression was carried out for individuals who had a PHQ2<5 and PHQ2<4 at baseline.

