8.3.1.2 Exclusion Criteria

- Patients ineligible for the standard IAPT care pathway;
- Patients with previous and current known major mental illness such as Schizophrenia, severe depression, any co-morbid neurological or neuro-psychiatric condition such as epilepsy;
- Patients with current psychosis or a history of psychotic symptoms within the last 6 months
- Patients with suicidal ideation;
- Patients scoring > 15 points on PHQ- 9;
- Patients scoring > 15 points on GAD- 7;
- Patients with significant cognitive disorders;
- Patients with noted neurodevelopmental conditions such as autism or ADHD;
- Patients previously diagnosed with a personality disorder;
- Patients who been under the care of CMHT or a specialised mental health services in the last 2 years;
- Patients who failed IAPT previously;

- Patients with referrals for specialist presentations of pre-existing, diagnosed conditions requiring a specialised assessment beyond the standard clinical pathway;
- Incapable of self-consent;
- In a dependent/unequal relationship with the research or care teams or any PPI representatives.

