8.3.2 Sampling

8.3.2.1 Sample Size

Approx 1100 eligible patients are seen per month at the IAPT in the CNWL NHS Foundation Trust. Preliminary work suggests that Wysa is associated with a mean clinical improvement in PHQ-9 of 5.84 (SD6.66) [28]. This study is powered to detect a clinically meaningful effect on the PHQ-9 scale [28]. Based on a SD of 6.6 and a 2:1 recruitment ratio (usual care: intervention) a sample size of 393 would allow detection of a difference in PHQ-9 of at least 2 points, with 80% power. Augmenting the sample size to 480 would allow for 20% attrition, whilst still maintaining sufficient power to detect clinically and statistically meaningful differences with a Type 1 error rate of 0.05. This inflated sample size would also allow for adjustment for stratification variables, gender, age, ethnicity, self-reported antidepressant use, and severity of depression.

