8.4 Data Collection

8.4.1 Randomisation

8.4.1.1 Sequence Generation

Demographic data will be collected from all patients immediately after they complete the informed consent process, during the same phone call. Together with data from the IAPT referral, this information will be used in the randomisation algorithm to ensure that the intervention and control groups are balanced on key variables (gender, age, ethnicity, self-reported antidepressant use, and severity of depression).

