8.4.1.2 Allocation Concealment Mechanism

Consenting participants will be inputted into a masked computer randomisation algorithm and the outcome will be recorded in an electronic record to conceal treatment allocation from study researchers. Participants will be sent an automatic email to inform them of their group assignment, and participants in the intervention group will receive the link to download Wysa.

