8.4.3.1 Quantitative data collection

The quantitative outcome measures will be delivered directly to patients through the Wysa app or by Qualtrics survey (e.g. for participants in the control group). Participants in both conditions will complete four questionnaires at baseline and 3-months post-randomisation (PHQ-9, GAD-7, EQ-5D-5L, and SF-12). Outcome measures have been chosen that will not be a significant burden for participants to complete; none of the questionnaires are longer than 12 items or expected to take more than a few minutes each to complete. Together, the questionnaires should take participants from 10 to 20 minutes to complete. Patient responses will be automatically uploaded to the iaptus electronic patient records using the Mayden Prism API. App use data will be automatically stored through the app.

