8.5 Data Analysis

8.5.1 Statistical Methods for Primary Outcome

Descriptive statistics will be used to characterise users, assess baseline comparability, and compare side effects. Primary comparisons between intervention and control groups will be conducted for primary and secondary outcomes. Primary analyses are designed with 80% power to detect a two-sided α of 0.05. All analyses will report 95% CI around estimate of effect. Comparative analyses will be conducted on an intention to treat basis, using linear or logistic regression, with adjustment for stratification variables.

We will explore missingness in our data, be that in relation to primary outcomes, follow-up data and in WYSA analytic information. The proportion of missing data will be explored and reported on descriptively. An hypothesised scenario, where patients remove themselves from the waiting list for treatment before the duration of follow-up may lead to missing data scenario. Currently, estimates

suggest that xxx% of our cohort will 'drop-off' waiting list before our primary endpoint. We will conduct exploratory sensitivity analyses in a complete case ('per protocol') cohort compared with the ITT analysis.

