8.5.2 Other Data Analyses

Secondary analyses will include additional adjustment for factors showing possible imbalance at baseline and pre-planned exploratory analyses for differential effects of the intervention for different age groups, depression severity, and interaction (dose) of the Wysa app. Secondary analyses including adjustment for factors showing potential imbalance at baseline and pre-planned exploratory subgroup analyses for differential effects in a priori specified groups will be conducted using linear or logistic regression. For secondary analyses, where we have not specifically powered the study to detect statistical or clinical meaningful differences, we will report p-values but will focus on interpretation of 95% CI around estimates.

The qualitative semi-structured interviews will be evaluated using a thematic analysis.

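### The SAP's PHQ-9 model sentence names only the two arms and neither restates nor withdraws the protocol's adjustment for the five allocation factors, so the primary model is unsettled and some precision may be lost.

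*SAP*

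**What the plan says.** Protocol 8.5.1 sets the model: "Comparative analyses will be conducted on an intention to treat basis, using linear or logistic regression, with adjustment for stratification variables". Protocol 8.3.2.1 lists the factors when it says the enlarged sample "would also allow for adjustment for stratification variables, gender, age, ethnicity, self-reported antidepressant use, and severity of depression". Protocol 8.4.1.1 gives the same five as the variables that the allocation algorithm balances, and the SAP repeats them in its own paragraph on sequence generation.

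The SAP, dated 8 August 2023, is later than protocol version 1.1 (29 September 2022). Its only sentence on the PHQ-9 and GAD-7 models, under Statistical methods, is: "Linear regression was used to carry out comparative analysis of the primary outcome PHQ9, and secondary outcome GAD7, to compare the two treatment arms". It gives no covariates, does not refer back to 8.5.1 and does not say that the adjustment was abandoned. Neither document says how age, ethnicity or severity would be coded in the model.

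**The concern.** Two analysts working from these documents could fit different primary models and report different estimates and confidence intervals. One would adjust for five factors, as the protocol requires. The other would compare the arms alone, as the SAP's wording suggests.

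The choice matters because severity at entry is likely to predict severity at three months. An arm-only model leaves that variation in the residual. If allocation has also balanced severity, the variation no longer contributes to the difference between arms, yet the arm-only standard error still counts it. The interval is then wider than it should be and the test rejects too rarely. If allocation was in effect simple randomisation, the arm-only test keeps its nominal level and the loss is only in precision and power.

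**Working it through.** **Reproducing the planned sample size.** Inputs from protocol 8.3.2.1 and 8.5.1: difference 2 points, 2:1 allocation, 80% power, two-sided 0.05, so the normal quantiles sum to 2.8016. The smaller arm is 1.5 × (SD × 2.8016 / 2)².
- SD 6.66: 130.6, rounded up to 131; total 3 × 131 = 393, as stated.
- SD 6.6: 128.2, rounded up to 129; total 387.

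No covariate reduction enters, so the planned power did not rely on adjustment.

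**Arm-only model.** Analysed: 480 × 0.8 = 384, split 128 and 256. The protocol and SAP give the 2:1 ratio in opposite directions, but this does not change the standard error. With SD 6.6:
- SE = 6.6 × √(1/128 + 1/256) = 0.7145
- 95% half-width = 1.96 × 0.7145 = 1.40 points
- power for 2 points with no balance: 79.7%

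**Adjusted model.** Let r be the correlation of pre-randomisation severity with 3-month PHQ-9, and k = √(1 − r²). The documents do not give r, so a range is shown.
- Adjusted half-width = 1.405 × k (1.405 is the arm-only value with the t quantile)
- Adjusted power: noncentral t, noncentrality 2 / (0.7145k)
- Arm-only under full balance: the true SE is 0.7145k but the reported SE is 0.7145. Type I error is therefore 2 × (1 − Φ(1.96/k)) and power is Φ((2/0.7145 − 1.96)/k).

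| r | k | Adjusted half-width | Arm-only type I error, full balance | Arm-only power, full balance | Adjusted power |
|---|---|---|---|---|---|
| 0.2 | 0.980 | 1.38 | 4.6% | 80.4% | 81.3% |
| 0.3 | 0.954 | 1.34 | 4.0% | 81.1% | 83.3% |
| 0.4 | 0.917 | 1.29 | 3.2% | 82.0% | 86.1% |
| 0.5 | 0.866 | 1.22 | 2.4% | 83.4% | 89.7% |
| 0.6 | 0.800 | 1.12 | 1.4% | 85.3% | 93.7% |

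For r = 0.2 to 0.4 the interval narrows by 2% to 8% (1 − k). The power gain is 0.9 to 4.1 percentage points under full balance. Against 79.7% with no balance it is 1.6 to 6.4.

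**Which r is plausible.** The exclusion "Patients scoring > 15 points on PHQ- 9" restricts the range of baseline severity and so lowers r. As an illustration, suppose r would be 0.5 without the cap and the cap cuts the baseline SD to a fraction u = 0.6 to 0.8 of its former value. Then r·u/√(1 − r² + r²u²) gives 0.33 to 0.42, for a gain of about 2.7 to 4.5 points under full balance.

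**Simulation check.** 2,500 trials per setting were run with 384 patients and five factors that explain a share R² of the outcome variance.
- Under biased-coin minimisation, R² of 0.1 and 0.2 gave arm-only null rejection rates of 4.0% and 2.9%, against 5.1% and 5.0% adjusted.
- Under simple randomisation, the arm-only rate stayed between 4.2% and 5.4% for R² from 0 to 0.4.

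**The case against.** The strongest defence is that the SAP's statistical section is one short paragraph and may be shorthand. It also omits intention to treat, the 95% CI and missing data, all of which protocol 8.5.1 covers, and nothing in it claims to replace the protocol. That stands as far as it goes. A reader might infer that an unadjusted model was run, and the documents do not show that. But a later document, written largely in the past tense, that describes the primary model without its covariates leaves the question open.

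The defence is also right that the effect is limited and conditional. Neither document names the allocation method, so conservatism cannot be asserted outright. The SD of 6.6 is an assumption for the 3-month score, because protocol 8.3.2.1 gives 6.66 as the SD of improvement. If the 3-month SD were 5 to 6 (also an assumption), arm-only power with no balance would already be 96% to 87%, leaving less to gain. The proportional narrowing of the interval depends only on r.

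Two stronger readings should be resisted.
- A reader might infer that the severity covariate could be recorded after allocation. The trial questionnaires are "delivered directly to patients through the Wysa app or by Qualtrics survey (e.g. for participants in the control group", and on notification of assignment "participants in the intervention group will receive the link to download Wysa". But the collection timeline is in Figure 5, which is not reproduced in the text reviewed. The stratification values precede allocation by construction: "Together with data from the IAPT referral, this information will be used in the randomisation algorithm". Screening against the PHQ-9 limit also implies an earlier score.
- A reader might ask for a severity interaction or a baseline GAD-7 term. Both go beyond this point, and protocol 8.5.2 already plans "pre-planned exploratory analyses for differential effects of the intervention for different age groups, depression severity, and interaction (dose) of the Wysa app".

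**Conclusion.** The point holds as a gap in specification with a modest, one-directional cost. The protocol commits to adjustment for five factors, and the SAP leaves unclear whether that was done. If it was not, and severity is prognostic, the result is less precise than the design allows. The test is conservative as well only if the algorithm delivered the stated balance.

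The comparison is not biased, type I error is not inflated, and arm-only power stays at about the planned 80%. The loss is relative to the adjusted model: a half-width of 1.40 instead of 1.38 to 1.29 points, and about 1 to 4 percentage points of power under full balance or 2 to 6 with none. These figures assume 384 analysed, a 3-month SD of 6.6 and r between 0.2 and 0.4. Gains are larger at higher r, but the PHQ-9 cap makes the low end plausible. The gap should be fixed; it does not threaten the trial's validity.

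**What to change.** State in the SAP that the primary model is linear regression of 3-month PHQ-9 on arm plus the five allocation factors, by intention to treat with a 95% CI, as protocol 8.5.1 provides. State the same covariates for the GAD-7 model. Use the values supplied to the randomisation algorithm and give the coding of age and ethnicity. Enter severity as the continuous pre-randomisation PHQ-9 score if it was kept.

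If the analysis already run was adjusted, the cost is a change of wording. If it was not, it needs one re-run with the adjusted model reported as primary, and disclosure of any covariate form chosen after data were seen. Someone must confirm that the allocation values were retained; both documents say severity fed the algorithm, so they should exist. No patients are added.

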7.5 Aims and Objectives

The primary aim of this project is to establish real-world efficacy that patient use of Wysa while waiting for treatment through the NHS mental health care pathway positively impacts well-being by comparing system users with standard services users.

The secondary aims of this project are:

1. To examine the feasibility of using Wysa to identify users at high risk of a mental health crisis and escalate them to further care;
2. To examine levels of user engagement with Wysa;
3. To evaluate patient acceptability of an autonomous early intervention supporting mental health services;
4. To complete a full health economic assessment of using Wysa for autonomous early intervention and triaging support;
5. To assess the potential for sustainable adoption of Wysa in mental healthcare pathways.

[figure not shown]

Figure 3. Wisconsin logic diagram

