Two questionnaires will be used to assess health-related quality of life: the EQ-5D-5L [40] and the Short Form 12 (SF-12) health survey [41]. The EQ-5D-5L provides a descriptive self-assessment of health in 5 dimensions: mobility, self-care, usual activities, pain/discomfort and anxiety/depression [40]. It is commonly used as a quality of life measure to conduct cost effectiveness analyses [42]. The EQ-5D-5L has a greater emphasis on physical than mental health, but has demonstrated the ability to capture changing anxiety severity [43]. The SF-12 survey is a reliable measure of functional health and is well-suited for this study, as it includes mental health items and has been shown to be acceptable for use as a screening tool for depressive disorders [44].

Cost-effectiveness

To conduct a health economic analysis, the study will collect data on health and social care service use, medication use and treatment costs, the implementation costs of Wysa, out of pocket medical expenses borne by patient and carers and productivity related costs such as work absence / time off work due illness. This data will be combined with the quality-of-life indicators to produce an assessment of the costs of adopting Wysa from the perspective of both the UK health and social care services and the wider society [45]. This analysis will also produce a budget impact model for each site that will be used to provide a final overall implementation strategy for more rapid adoption at other NHS sites and dissemination across the AHSN network in partnership with the new Integrated Care Systems. The team will also incorporate the environmental sustainability calculation in line with the Greener NHS agenda.

Table 6. Secondary Outcome Measurement

Secondary Outcome	Outcome Measure
Anxiety severity	
 Score on the GAD-7 [37]
Crisis identification	
 Number of users identified by the app for escalation of care compared to the number of patients in the control group who access A&E or out-of-hours services while waiting for treatment
Engagement	
 Uptake rates Dropout / 'did not attend' rates App usage data Qualitative feedback from semi-structured interviews
Acceptability	
 Qualitative feedback from semi-structured interviews Automated review questions periodically requested during general use of the tool

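### The SAP specifies arm comparisons only for PHQ-9 and GAD-7, so, followed as written, it gives no between-arm estimate for the protocol's quality-of-life outcome (EQ-5D-5L and SF-12)

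*SAP*

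**What the plan says.** Protocol 8.2.5.2 and Table 6 list health-related quality of life as a secondary outcome, measured by EQ-5D-5L and SF-12. Section 8.4.3.1 schedules both scales in both arms: "Participants in both conditions will complete four questionnaires at baseline and 3-months post-randomisation (PHQ-9, GAD-7, EQ-5D-5L, and SF-12".

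Protocol 8.5.1 states what will be compared: "Primary comparisons between intervention and control groups will be conducted for primary and secondary outcomes". It also states how: "Comparative analyses will be conducted on an intention to treat basis, using linear or logistic regression, with adjustment for stratification variables". Section 8.5.2 adds that secondary analyses, which were not powered, will be read mainly through their 95% confidence intervals.

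The fourth secondary aim in 7.5 is economic: "To complete a full health economic assessment of using Wysa for autonomous early intervention and triaging support". Section 8.2.5.2 links it to the same scales, saying of the cost data: "This data will be combined with the quality-of-life indicators to produce an assessment of the costs of adopting Wysa".

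The SAP, dated 8 August 2023, says under Statistical methods: "Linear regression was used to carry out comparative analysis of the primary outcome PHQ9, and secondary outcome GAD7, to compare the two treatment arms". On other secondary outcomes it offers only a description: "Descriptive statistics was used to assess baseline comparability and the distributions of the primary and secondary outcomes". It adds post hoc regressions in participants below two baseline PHQ2 cut-offs. It does not name EQ-5D-5L, SF-12, costs or any economic plan.

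**The concern.** The protocol promises an arm comparison for every secondary outcome, and the SAP delivers one for a single secondary scale. An analyst who worked from the SAP alone would produce no treatment effect on quality of life. The link between quality of life and the economic assessment would also have no detailed analysis behind it.

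The timing makes the silence matter more. The SAP's statistical section describes analyses as already carried out. It finds room for regressions that it calls post hoc, but not for a comparison that the protocol had promised. A reader cannot tell whether the quality-of-life scales were compared and not mentioned, not collected well enough to use, or left out for some other reason. Protocol 10.1 says the data will also support a device approval, so the readers affected include a regulator.

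**Working it through.** The main check sets the two documents side by side. No arithmetic is needed for it.

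| Questionnaire | Role in protocol | Scheduled in both arms, baseline and 3 months (8.4.3.1) | Arm comparison promised (8.5.1) | Arm comparison named in SAP |
|---|---|---|---|---|
| PHQ-9 | Primary | Yes | Yes | Yes |
| GAD-7 | Secondary | Yes | Yes | Yes |
| EQ-5D-5L | Secondary | Yes | Yes | No |
| SF-12 | Secondary | Yes | Yes | No |

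Two of four have no arm comparison in the SAP, and together they make up the whole quality-of-life outcome. The SAP's descriptive sentence does not fill the gap, because describing a distribution gives no estimate of a treatment effect with an interval.

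The second check asks whether sample size could justify leaving the scales out. The inputs, from protocol 8.3.2.1 and 8.5.1, are a difference of 2 points, two-sided alpha 0.05, 80% power, 2:1 allocation, an SD of 6.6 (6.66 in the preliminary work), 393 evaluable, 480 recruited and 20% attrition.

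1. Reproduce the plan's figure. Smaller arm n = (1.960 + 0.842)² × (1 + 1/2) × (SD/2)².
   - SD 6.66: n = 131, total 3 × 131 = 393, which matches exactly.
   - SD 6.6: n = 129, total 3 × 129 = 387, within 2% of 393.
2. Number analysed after attrition: 480 × 0.80 = 384, split 128 and 256.
3. Standardised difference detectable with 80% power on any continuous outcome, unadjusted: (1.960 + 0.842) × √(1/128 + 1/256) = 2.802 × 0.1083 = 0.303 SD.

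For comparison, the primary target is 2/6.6 = 0.303 SD. A quality-of-life comparison would thus have about the same standardised sensitivity as the primary one, if follow-up is equally complete. The protocol and SAP state the 2:1 ratio in opposite directions. They must be reconciled, but step 3 is the same whichever arm is larger.

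**The case against.** A reader might infer that the quality-of-life comparisons were never made and that the economic aim goes unanswered. The documents do not support that. Protocol 8.5.1 still covers these outcomes in general terms, and the SAP does not withdraw that commitment or say that anything was dropped. The economic assessment also rests on service use, medication, implementation, patient-borne and productivity costs and on a budget impact model (8.2.5.2). Protocol 10.1 attributes that model to a work package, so a separate plan may exist outside these documents. Two regressions on questionnaire scores would not deliver the economic aim in any case.

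A reader might also infer that GAD-7 was picked, or the other scales dropped, because of the results. The documents do not show this either. GAD-7 is the first secondary outcome in 8.2.5.2, section 8.2.5.1 pairs it with PHQ-9 as a routine IAPT measure, and the study summary frames the aim around depression and anxiety. The past tense shows when the text was written, not why an outcome is missing. No results report is available.

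Nor are the PHQ2 regressions wholly foreign to the protocol. Section 8.5.2 plans exploratory analyses by depression severity. Only the specific cut-offs are new, and the SAP itself calls these regressions post hoc.

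Finally, the SAP does not confirm that EQ-5D-5L and SF-12 were actually obtained, or how completely.

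All of this stands, and it limits what can be claimed. It does not close the gap. The general sentence in 8.5.1 does not say which score of each scale is analysed, and the later, more specific document names two scales and passes over the other two without a reason.

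**Conclusion.** The point holds as a mismatch between protocol and SAP. A named secondary outcome, measured by two of the four questionnaires scheduled in both arms, has no arm comparison in the SAP, no stated reason for that, and no reference to another plan. Selective reporting cannot be ruled out from these documents and is not shown by them. The economic aim has no detailed plan in view, but it should not be called blocked.

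The primary PHQ-9 analysis is unaffected, so this is a change that should be made rather than one on which the trial's main conclusion depends. The figure of about 0.30 SD assumes 384 analysed at 2:1, no covariate adjustment and quality-of-life follow-up as complete as planned for PHQ-9. The documents give no target difference for either scale, so whether 0.30 SD is adequate cannot be judged from them.

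**What to change.** 1. Add to the SAP, for the EQ-5D-5L and SF-12 scores at 3 months, the intention-to-treat linear regression of protocol 8.5.1. Adjust for the stratification variables (age, gender, ethnicity, depression severity and reported antidepressant use). Include each scale's own baseline score and declare it as a covariate added to the protocol model. Name the score analysed for each scale. Report estimates with 95% confidence intervals, as 8.5.2 directs.
2. Write the model out in full. The SAP states no analysis set or covariates even for PHQ-9, so a reference to the same model would leave both undefined.
3. List every Table 6 outcome in one table, marking any not analysed or not collected and giving the reason.
4. Cite the health-economic analysis plan, or state that there is none.
5. Label analyses that appear only in the SAP, including the PHQ2 cut-off regressions, as post hoc wherever they are reported. Because the SAP's statistical section is in the past tense, the newly written detail in item 1 should be dated, with protocol 8.5 identified as the earlier commitment.

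The cost is a few lines of text, one table and two regressions on questionnaires that the protocol already schedules, with no change to sample size. If either scale was not collected, the cost is a sentence saying so. The downside is that null or unfavourable quality-of-life results must be shown.

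### The SAP does not mention the protocol's pre-planned subgroup analyses, and its two nested post hoc PHQ2 regressions cannot show whether the effect differs by severity

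*SAP*

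**What the plan says.** Protocol section 8.5.2 commits to "pre-planned exploratory analyses for differential effects of the intervention for different age groups, depression severity, and interaction (dose) of the Wysa app". It adds that "pre-planned exploratory subgroup analyses for differential effects in a priori specified groups will be conducted using linear or logistic regression". It gives no severity cut-points and names no treatment-by-severity term. For analyses that the study was not powered for, it says "we will report p-values but will focus on interpretation of 95% CI around estimates".

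The SAP, under Statistical methods, describes the main analysis: "Linear regression was used to carry out comparative analysis of the primary outcome PHQ9, and secondary outcome GAD7, to compare the two treatment arms". It then says: "Additional post hoc regression was carried out for individuals who had a PHQ2<5 and PHQ2<4 at baseline". It does not mention the age, severity or app-use analyses, either as done or as dropped. For the PHQ2 regressions it states no outcome, no reason for the cut-offs, no interaction term, no result for participants at or above each cut, and no approach to multiplicity.

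PHQ2 appears nowhere in the protocol. Severity there means the PHQ-9, one of the instruments covered by "Participants in both conditions will complete four questionnaires at baseline and 3-months post-randomisation". Severity also entered the randomisation, which was to keep the arms "balanced on key variables (gender, age, ethnicity, self-reported antidepressant use, and severity of depression".

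**The concern.** The protocol asks whether the effect of the app differs by baseline severity. A treatment comparison inside one subset estimates the effect in that subset and compares it with nobody else's. A significant result among participants with low PHQ2 scores could therefore be taken to show that milder cases benefit more when the data do not show it.

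The two regressions are also two further unadjusted looks at the treatment effect, on a score and cut-offs that the reader cannot trace. At stake are the reading of the subgroup results and the protocol's question of who benefits. The primary comparison itself is not at stake.

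**Working it through.** **Inputs.** Protocol 8.3.2.1 gives SD 6.6, a 2-point difference, 2:1 allocation, 80% power and 393 evaluable participants, "with a Type 1 error rate of 0.05". Protocol 8.5.1 makes the test two-sided. The SAP states the 2:1 ratio in the opposite direction to the protocol, but with equal SDs this does not change the formulas. Subset sizes are not given, so I assume that PHQ2<5 holds 40% to 90% of the 393 and PHQ2<4 holds 20% to 80%. I also assume SD 6.6 and 2:1 allocation within each subset.

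**1. The plan's own figure.** With 2:1 allocation, the variance of the difference is SD² × (3/N + 1.5/N) = 4.5 × SD²/N. So N = 4.5 × [6.6 × (1.960 + 0.842)/2]² = 384.6, or 129 + 258 = 387 with whole arms. SD 6.66, which the protocol also quotes, gives exactly 393. The figure reproduces. At N = 393 the SE is 6.6 × √(4.5/393) = 0.706 and power for 2 points is 81%.

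**2. Power within a subset.** For share f, the SE is 0.706/√f. Power for 2 points is 43% to 77% in PHQ2<5 and 24% to 72% in PHQ2<4.

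**3. Does subset significance indicate a differential effect?** Suppose that everyone has the same 2-point effect. The subset and its complement are independent, so P(subset significant, complement not) = power(f) × [1 − power(1 − f)].

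| Subset share | Power, subset | Power, complement | P(subset significant, complement not) |
|---|---|---|---|
| 40% | 0.433 | 0.592 | 0.433 × 0.408 = 0.18 |
| 60% | 0.592 | 0.433 | 0.592 × 0.567 = 0.34 |
| 80% | 0.717 | 0.244 | 0.717 × 0.756 = 0.54 |

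Simulation with 1,000,000 draws gives the same values. The contrast arises often when no difference in effect exists.

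**4. False-positive chance.** Under no effect, the two subset statistics correlate at √(share of PHQ2<4 / share of PHQ2<5), and each correlates with the full-sample test at √(its share). Simulation with 1,000,000 draws, each test at 0.05:

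| PHQ2<5, PHQ2<4 shares | Two subset tests | With the primary test |
|---|---|---|
| 90%, 80% | 6.5% | 7.8% |
| 80%, 60% | 7.3% | 9.1% |
| 70%, 50% | 7.5% | 9.8% |
| 60%, 40% | 7.7% | 10.4% |
| 50%, 25% | 8.3% | 11.3% |
| 40%, 20% | 8.3% | 11.7% |

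Independent tests would give 1 − 0.95² = 9.75% and 1 − 0.95³ = 14.3%, so the overlap lowers the inflation. If the subset regressions were run on both PHQ-9 and GAD-7 (assumed correlation 0.6), the four tests give 11.3% to 14.2%.

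**5. What an interaction test could detect.** For two severity groups, the SE of the difference in effect is 0.706 × √(1/f + 1/(1 − f)).
- At f = 0.5 it is 0.706 × 2 = 1.41. Power for a 2-point difference in effect is 29%, and the difference detectable with 80% power is 2.80 × 1.41 = 4.0 points.
- At f = 0.9 it is 0.706 × 3.33 = 2.35. Power is 14%, and the detectable difference is 6.6 points.

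**The case against.** The SAP labels these regressions post hoc and additional, and never says that they test a differential effect. The protocol calls its own subgroup work exploratory and puts the weight on confidence intervals. It sets no cut-points and no interaction term, so part of the gap begins there. The SAP is equally silent on age and app use, which fits a brief document. The inflation is modest, and the interaction test is itself weak. All of this stands, and it limits the point to reporting and interpretation.

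The objection does not supply the missing analysis. The post hoc label tells the reader about timing. It does not define PHQ2, explain the cut-offs or allow a comparison across severity.

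A reader might infer more than the documents support:
- **That the PHQ2 regressions replace the severity analysis.** The SAP calls them additional and does not say that anything was dropped.
- **That the cuts were chosen because they favour the app, or to rescue a null result.** The documents give neither the results nor how the cuts were chosen.
- **That PHQ2 was never collected.** It is undefined, and nothing says how it was obtained.

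**Conclusion.** The point holds as a gap in the analysis plan and its reporting. The SAP leaves three pre-planned exploratory analyses unaccounted for. Its one severity-related analysis cannot answer the severity question as described. The misleading pattern of a significant subset beside a non-significant complement would occur in roughly 18% to 54% of trials with a uniform 2-point effect.

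The extra false-positive risk is real but small, and the primary test keeps its own 5% error rate. A data-driven choice of cut-offs would add to the risk, but the documents do not let that be measured or show that it happened.

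The percentages rest on assumed subset shares and on SD 6.6 within subsets. The logical point, that one-sided subset regressions do not test a difference in effect, needs neither assumption.

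**What to change.** Keep the SAP sentence, because it discloses an analysis that was done, and add the following:
- **Severity.** Fit an intention-to-treat linear regression of three-month PHQ-9 on treatment, continuous baseline PHQ-9, their interaction and the stratification variables. Report the interaction as an estimate with 95% CI, with fitted treatment effects at several baseline values across the enrolled range (protocol 8.3.1.2 excludes scores above 15).
- **Age.** Report the pre-planned analysis in the same way.
- **App use.** Report the pre-planned analysis or state that it was not done.
- **PHQ2 subsets.** Define the score, name the outcome, give the reason for each cut-off, show results on both sides of each cut, label them hypothesis-generating, and do not base the trial's conclusion on them.

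The cost is SAP wording and a few regressions on data that the protocol already collects. The drawback is low power, about 14% to 29% for a 2-point difference in effect between two severity groups. The SAP should therefore say that a non-significant interaction is not evidence of a uniform effect.
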